8.7 Subject Disposition and Dosing Summary

All subjects enrolled in the study (i.e., who sign informed consent and complete inclusion/exclusion criteria) will be included in the summary of subject disposition and accountability. No inferential statistical tests will be performed. The tabulation of number of subjects in each treatment group and overall will be displayed for all subjects in the Safety Population, in the ITT Population, and in the PP Population. The number and percent of subjects

who completed or discontinued the study will be displayed for each treatment group and overall together with reasons for early termination, where the percent is with respect to the total number of randomized subjects in that treatment group. The timepoint of doses and total MDMA (mg) administered will be summarized by treatment group for the Safety, ITT and PP Populations.

8.8 Demographics and Baseline Characteristics

Subject demographic data and baseline characteristics will be summarized descriptively by treatment group and overall. The demographic data and baseline characteristics will be summarized for the ITT and Crossover Populations.

8.9 Prior and Concomitant Medications

The number and percent of subjects who took medications prior to and after signing informed consent will be summarized descriptively for each treatment group. Concomitant medications will be summarized similarly. Prior and concomitant medications will be summarized for the Safety Population. Psychiatric medications will be coded to common drug classes and terms.

8.10 Efficacy Analyses

For all primary, secondary and exploratory endpoints descriptive statistics (n, mean, standard deviation, median, range, or counts and percentages where appropriate) will be provided by treatment group.

8.10.1 Primary Efficacy Analyses

Liebowitz Social Anxiety Scale (LSAS)

The primary efficacy evaluation is the change from baseline to the primary outcome timepoint (visit 13, one month post experimental session 2) in the LSAS score of Social Anxiety (difference score). The primary efficacy comparison on difference scores will be made with independent sample t-tests at an alpha level of 0.05. If the primary hypothesis rejects, pairwise comparisons among the treatment groups will be made with t-tests. If the parametric assumptions for the t-test analyses are not met, the analogous nonparametric methods will be used (Wilcoxon Rank Sum Test). If data has normal distribution, Cohen's d placebo-subtracted effect size will be estimated on mean difference scores from baseline to Visit 13 with confidence intervals.

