Upon enrollment, the first six subjects (Group 1) will be randomized to receive one dose of either placebo (N=2) or 75 mg MDMA (N=4). In the second experimental session one month later, Group 1 subjects randomized to MDMA will escalate to 100 mg MDMA, unless contraindicated by safety and tolerability concerns. The second six subjects (Group 2) will be randomized to receive one dose of either placebo (N=2) or 100 mg MDMA (N=4). In the second experimental session one month later, Group 2 subjects randomized to MDMA will escalate to 125 mg MDMA, unless contraindicated by safety and tolerability concerns. Subjects randomized to placebo in Group 1 and Group 2 will

receive placebo in both experimental sessions also scheduled one month apart. The blind will be maintained through the six-month follow-up for each individual subject, after which the blind will be broken. Placebo subjects will be offered an open-label extension (Stage 2) with two experimental sessions scheduled one month apart, in addition to three hour-long integrative sessions during the month after each experimental session. Stage 2 subjects will receive 75 mg MDMA in the first experimental session and will escalate to 125mg MDMA in the second experimental session, unless contraindicated by safety and tolerability concerns from other subjects in Stage 1.

During experimental sessions, there will be periods of structured and unstructured interactions. The structured interactions will be selected based on elements of therapeutic interventions that are currently in use in this population for the treatment of social anxiety and to enhance functional skills [7]. The unstructured interactions will include an array of therapeutic activities and approaches that would be appropriate for subjects to engage in during experimental sessions. All subjects will follow the same schedule of structured alternating with unstructured periods but will be able to choose from a selection of activities during each unstructured period. Examples include, but are not limited to, working with art supplies, listening to preselected music, writing in journals, silent introspection, and engaging in rapport-building interactions with researchers.

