12.0 Data Analysis

This study is primarily a safety study that will also obtain estimates of effect size comparing MDMA vs. placebo using observer-blind data from the LSAS as the primary outcome measure. MDMA doses are not expected to differ greatly in treatment outcomes and will be combined for effect size estimates. Descriptive statistics will be computed overall for MDMA and placebo, and within the MDMA dose groups for all available data from outcome measures, including minimum, maximum, average, and standard deviation. Distributional characteristics will be examined for outliers and extreme values and, if either is evident, nonparametric statistics will be utilized in the analysis. Effect size for all outcome measures will be estimated using Cohen's techniques.

The sponsor will examine MDMA and placebo groups for homogeneity through comparing demographic characteristics. There is no expectation that conditions will differ in composition by gender, race or ethnicity, duration of autism diagnosis, or presence versus absence of other permitted psychiatric disorders, such as depression. However, owing to small sample size, such variations may arise by chance. If MDMA and placebo subjects differ upon a demographic variable, then the effects of this variable will be taken into account when looking at safety analyses. No systematic differences are expected.

Primary and secondary outcome measure scores will be plotted across each time of administrations for trend analyses. The number of intervals will vary in accordance with times listed for each measure, but will include in most cases baseline, one or more times after the first experimental session, one or more times after the second experimental session and at six month follow up. Plots will be made for MDMA and placebo subjects, and if trends occur for MDMA subjects, separate exploratory plots will be made for outcome measures after 0, 75, 100 and 125 mg MDMA.

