2.0 Introduction

This document presents a Statistical Analysis Plan (SAP) for MAPS study protocol MAA-1, a Phase 2 pilot clinical trial designed to evaluate the safety, feasibility, and efficacy of MDMA-assisted psychotherapy in treating social anxiety in adults on the autism spectrum.

The Multidisciplinary Association for Psychedelic Studies (MAPS) is a non-profit research and educational organization working to obtain approval for the prescription use of 3,4-methylenedioxymethamphetamine (MDMA)-assisted psychotherapy in adults on the autism spectrum with social anxiety. This is an initial pilot study to assess the efficacy of MDMA for this indication, following promising results from MAPS-sponsored studies of MDMA-assisted psychotherapy for posttraumatic stress disorder (PTSD).

The Phase 2 pilot study will examine the safety, feasibility, and efficacy of MDMA-assisted psychotherapy for social anxiety in 12 MDMA-naïve adults on the autism spectrum. This study is designed as a dose escalation study to assist with the exploration of safety and finding the most effective dose in this population. Subjects assigned to the MDMA group will receive two of three different doses, either 75 mg, 100 mg, or 125 mg MDMA. Overall, eight subjects (66.7%) will be randomized to the MDMA group and four subjects (33.3%) will be randomized to the placebo group. Subjects who received the placebo during Stage 1 will have the opportunity to cross over and take part in a second study segment, referred to as Stage 2, with two open-label experimental sessions, after completing the six-month follow-up visit at the end of Stage 1.

This study is designed to obtain safety data, and secondarily estimates of effect size for efficacy. The data will be used to determine study design and dosing for future studies for this indication. MAA-1 is also intended to contribute to the development of a manualized psychotherapeutic approach to this potential treatment. This study is exploratory. As a result, the sponsor will perform tests on all statistical comparisons without correcting for multiple comparisons.

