4.0 Study Design

This randomized, double-blind, placebo-controlled study will examine the safety, feasibility, efficacy of MDMA-assisted psychotherapy in twelve adults on the autism spectrum with social anxiety. Each of the 12 subjects will participate in two experimental drug-assisted (MDMA or placebo) therapy sessions of seven hours in duration within a brief course of non-drug therapy, including three preparatory sessions at the start of the study and three integrative sessions during the month after each experimental session.

Upon enrollment, the first six subjects (Group 1) will be randomized to receive one dose of either placebo (N=2) or 75 mg MDMA (N=4). In the second experimental session one month later, Group 1 subjects randomized to MDMA will escalate to 100 mg MDMA, unless contraindicated by safety and tolerability concerns. The second six subjects (Group 2) will be randomized to receive one dose of either placebo (N=2) or 100 mg MDMA (N=4). In the second experimental session one month later, Group 2 subjects randomized to MDMA will escalate to 125 mg MDMA, unless contraindicated by safety and tolerability concerns. Subjects randomized to placebo in Group 1 and Group 2 will receive placebo in both experimental sessions also scheduled one month apart. The blind will be maintained through the six-month follow-up for each individual subject, after which the blind will be broken. Placebo subjects will be offered an open-label extension (Stage 2) with two experimental sessions scheduled one month apart, in addition to three hour-long integrative sessions during the month after each experimental session. Stage 2 subjects will receive 75 mg MDMA in the first experimental session and will escalate to 125mg MDMA in the second experimental session, unless contraindicated by safety and tolerability concerns from other subjects in Stage 1. Subjects will attend a 1-hour follow-up integrative therapy session on the day after the experimental session. Two additional integrative sessions will be conducted within the month following each experimental session, prior to outcome assessments being conducted one month after each experimental session.

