5.0 Randomization and Blinding

This is a randomized, double-blind, placebo-controlled study with an open-label cross-over segment. For Stage 1, a randomization list will be prepared at the beginning of the study. If needed, subsequent randomization lists will be created to replace subjects who withdraw from the study to ensure that replacement subjects are not added to the end of the initial list. Each subject will be assigned to one of the two dose conditions: 0 mg (placebo) or 125 mg (full dose). Eight evaluable subjects will be assigned to the full dose condition, and four to the placebo condition. The study will employ a blinded randomization procedure that will maintain the 8:4 ratio while maintaining the blind and ensuring that each subsequent condition assignment is not predicated on the previous assignment.

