8.0 Analyses

In general, nominal variables will be described in terms of frequencies and percentages and analyzed using chi square analysis. Ordinal and non-normal continuous variables will be described using sample median and range, and analyzed by non-parametric statistical tests, and approximately normal variables will be described using sample mean and standard deviations and analyzed by parametric statistical tests. All statistical tests will be two-sided. All p-values will be rounded to and displayed in four decimals. If a p-value less than 0.0001 occurs it will be shown in tables as <0.0001. For any analysis that is called out as parametric, e.g. t-test, the parametric assumptions will be examined. If necessary, nonparametric analyses will be utilized, e.g. Wilcoxon rank-sum test.

Clinical data will be presented in tabular format. Data not subject to analysis according to this plan will not appear in any tables or graphs, but will be included in the data listings. Analyses will be carried out with SAS Version 9.3 or higher. Selected results may be presented graphically using standard graphical software.

Post-hoc exploratory analyses not identified in this SAP may be performed to further examine the study data. These analyses will be clearly identified as such in the final clinical study report.

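### Subjects are randomised 4:2 within each of two consecutive cohorts, but the primary test ignores Group, so a material Group difference makes it conservative and shrinks Cohen's d

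*SAP*

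**What the plan says.** On allocation, SAP 4.0 states that "the first six subjects (Group 1) will be randomized to receive one dose of either placebo (N=2) or 75 mg MDMA (N=4", and Protocol 4.0 continues: "The second six subjects (Group 2) will be randomized to receive one dose of either placebo (N=2) or 100 mg MDMA (N=4". The dose tables (Protocol Table 1, SAP Table 1) repeat the same 4 and 2 cells. In total, "eight subjects (66.7%) will be randomized to the MDMA group and four subjects (33.3%) will be randomized to the placebo group".

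On analysis, SAP 8.10.1 takes LSAS change from baseline to Visit 13: "The primary efficacy comparison on difference scores will be made with independent sample t-tests at an alpha level of 0.05". If the parametric assumptions fail, "the analogous nonparametric methods will be used (Wilcoxon Rank Sum Test". SAP 8.0 adds: "All statistical tests will be two-sided". No Group term appears, and SAP 8.10.2 carries the same method to every secondary measure. Protocol 12.0 gives a reason for pooling: "MDMA doses are not expected to differ greatly in treatment outcomes and will be combined for effect size estimates".

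SAP 5.0 describes the allocation differently: "Each subject will be assigned to one of the two dose conditions: 0 mg (placebo) or 125 mg (full dose". It keeps an 8:4 ratio and mentions no cohorts.

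**The concern.** As SAP 4.0 describes it, Group is a restriction on the randomisation. The two cohorts are separated in time and, in the MDMA arm, by dose regimen. The documents also suggest how outcomes might drift between them. Protocol 2.1 lists refinement of the treatment method among the exploratory elements, Protocol 4.0 has the sponsor feeding back to the therapists from ongoing video review, and Protocol 4.1 expects at least 22 months.

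A test that ignores Group counts any such difference as noise. With 12 subjects this matters twice: the interval widens, and the SD that standardises Cohen's d is inflated. Protocol 12.0 and SAP 6.0 say the effect size will be used to plan later trials, so a shrunken d carries forward.

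**Working it through.** **Inputs.** From the documents: 4:2 in each of two cohorts, two-sided alpha 0.05, unadjusted t-test. The allocation arithmetic checks: 4 + 4 = 8 and 2 + 2 = 4, or 66.7% and 33.3%. There is no power figure to reproduce, because Protocol 12.1 says none was available. Assumed, because the documents give no LSAS SD, effect size or cohort shift: SD of change = 1, true d = 1.5, equal variances, and a Group difference from 0 to 1.5 SD.

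**1. Balance.** With no losses, each arm is half Group 1 and half Group 2. A shift g common to both arms adds g/2 to both means, so bias = 0.

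**2. Error term, common shift g.** The within-arm sum of squares gains 8(g/2)² + 4(g/2)² = 3g². On 10 df the expected pooled variance is 1 + 0.3g². With a Group term it is 1, on 9 df. The standard-error factor is √(1/8 + 1/4) = 0.612 for both. Root-mean-square half-widths:
- unadjusted: 2.228 × 0.612 × √(1 + 0.3g²), which is 1.364 at g = 0 and 1.556 at g = 1;
- with Group: 2.262 × 0.612 = 1.385 at any g.

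They are equal when 1 + 0.3g² = (2.262/2.228)², so g = 0.32 SD.

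**3. Simulation, common shift** (200,000 trials per row; mean widths run slightly below twice the root-mean-square half-width):

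| g (SD) | Type I error, unadjusted | Power at d = 1.5, unadjusted v Group | Mean CI width, unadjusted v Group |
|---|---|---|---|
| 0 | 5.1% | 60% v 59% | 2.66 v 2.69 |
| 0.5 | 4.4% | 57% v 59% | 2.76 v 2.69 |
| 1 | 2.9% | 49% v 59% | 3.04 v 2.70 |
| 1.5 | 1.4% | 38% v 59% | 3.46 v 2.69 |

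Type I error with the Group term is 5.0% in every row.

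**4. Cohen's d.** At g = 1 the standardising SD is √1.3 = 1.14 times too large, so d is multiplied by 1/1.14 = 0.88, about 12% smaller. Because n scales with 1/d², a trial sized on it would be about 30% larger.

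**5. Difference h confined to the MDMA arm** (a pure regimen effect). The unadjusted sum of squares gains 8(h/2)² = 2h². The Group model keeps only the interaction part, h²/(1/4 + 1/4 + 1/2 + 1/2) = 0.67h². At h = 1, mean CI width is 2.92 v 2.79 and power 52% v 56%. At h = 0.5 the models are level (58% v 58%).

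**6. Loss of one Group 2 placebo subject.**
- Common shift: the unadjusted estimate moves by g(1/2 − 1/3) = 0.17g. The Group model is unbiased.
- MDMA-arm-only difference, h = 1, average effect 1.5 (1.0 in Group 1, 2.0 in Group 2): the unadjusted estimate stays at 1.5. The Group model weights the cohorts by 4×2/6 = 1.333 and 4×1/5 = 0.8, giving (1.333×1.0 + 0.8×2.0)/2.133 = 1.375, a bias of 0.125h.

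If both Group 2 placebo subjects are lost, the biases are 0.5g (unadjusted, common shift) and 0.5h (Group model, estimate 1.0).

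**7. If allocation were one unblocked 8:4 list,** the chance of exactly two placebo subjects per cohort is 15²/495 = 45%. A cohort shift could then reach the unadjusted estimate without any dropout.

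**The case against.** Pooling is a stated choice, in an exploratory pilot that calls itself underpowered for small or moderate effects. There is one centre (SAP 8.5) and one therapist team (Protocol 5.2.1), so drift may be small, and below about 0.3 SD the planned test is as good or better. All of this stands. It makes the gain conditional. It does not explain why a factor built into the allocation is left out when including it costs so little.

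A reader might infer three stronger things.

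- *That any cohort shift makes the planned interval worse than the adjusted one.* It does not below 0.32 SD for a common shift, or below about 0.5 SD for a difference confined to the MDMA arm.
- *That dropout biases the unadjusted estimate and a Group term cures it.* Bias needs losses that differ across Groups between the arms. Dropout at random gives zero expected bias, although one realised loss still moves that trial's estimate. The plan also limits losses: replacement before session 1 (Protocol 5.4), a request for the final outcome assessment from those stopping before session 2 (Protocol 12.0), and assignment of early-termination data to a scheduled visit (SAP 8.2). Under a regimen difference confined to the MDMA arm, it is the Group model that is biased after placebo losses (step 6).
- *That the planned test inflates false positives.* With 4:2 intact it errs the other way.

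**Conclusion.** The point holds as one of efficiency and effect-size estimation. SAP 8.10.1 and its fallback ignore the cohorts within which Protocol 4.0 and SAP 4.0 randomise. A material Group difference then makes the test conservative, widens the interval and shrinks Cohen's d. At an assumed 1 SD common shift the loss is about 10 points of power, 13% of CI width (3.04/2.70) and 12% of d. For a difference of the same size confined to the MDMA arm it is about 4 points of power.

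These sizes rest on equal variances, true d = 1.5 and shifts that the documents do not supply. After unbalanced losses neither model is safe in every case, and Group cannot be read as cohort or as dose alone, because the two coincide in the MDMA arm. The conflict between SAP 5.0 and SAP 4.0 has to be settled as well, since the analysis should follow the allocation actually used.

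**What to change.** - In SAP 8.10.1 and 8.10.2, prespecify change ~ arm + Group as the model for the MDMA-placebo effect and its CI.
- Replace the rank-sum fallback with a Group-stratified one: a permutation test within Group (15 × 15 = 225 allocations) or van Elteren.
- Keep the plain t-test as a sensitivity analysis. State that after unbalanced loss either model can be biased, the unadjusted one under a shift common to both arms and the Group model under a regimen-only difference, so both results will be reported.
- State that Group is a nuisance term, confounded with regimen in the MDMA arm, and will not be interpreted.
- Reconcile SAP 5.0 with SAP 4.0 on both the allocation scheme and the dose conditions.

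The cost is SAP wording and one degree of freedom. The critical t rises from 2.228 to 2.262. With no shift the mean CI is about 1% wider (2.69 v 2.66) and power about one point lower.

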5.2 Study Procedures and Visit Descriptions

5.2.1 Prescreening and Screening

The therapist team for this study will consist of the PI, [name]., and co-investigator [name]. Candidate, and all study visits will be completed at Harbor-UCLA Medical Center. Prospective subjects will be prescreened by telephone or email according to an IRB-approved script to learn if they meet basic eligibility criteria. All individuals who are prescreened should be assigned a screening number and recorded on the Subject Screening Log where information on the selection of potential subjects in the trial should be collected.

Upon signing the IRB-approved informed consent form (ICF), the potential subject may commence study-related screening activities. The screening number should also be recorded on the signed ICF. If a subject is enrolled, the study staff should record the enrollment date and assign a subject number. If a subject is not enrolled, an explanation should be recorded on the Screening Log. A CRF will not be completed for subjects who are not enrolled. These subjects will only be documented on the Screening Log and Source Records. It is the responsibility of the PI to file the Screening Log in the investigator site file (ISF) to be readily available for on-site monitoring and/or inspection by relevant authorities. Screening may take place over more than one day and should be complete by up to two months prior to enrollment. If, after reviewing all information, the PI concludes that a subject is eligible, they will enroll the subject in the study. Visits will be scheduled consecutively, as described in the Time and Events Table.

- a. Explain and obtain written informed consent from the subject and Support Partner. Written informed consent must be obtained from the subject prior to performing any tests or evaluations for the study.
- b. Assign the subject a screening number. Complete the Screening Log.
- c. Review the ability of females of childbearing potential to become pregnant and their commitment to practice appropriate birth control, as determined by the PI for the treatment period of the study.
- d. Collect perceptions about the study using the Feedback Questionnaire.
- e. Administer C-SSRS to assess suicide risk.
- f. Administer the SCID-I-RV to assess co-morbid psychological disorders.
- g. Administer ADOS-2, Module 4 to confirm autistic status.
- h. A blinded IR will administer the LSAS.
- i. Obtain medical and psychological history by interview.

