5.2.2 Preparatory Sessions and Baseline Measures

Subjects who do not complete all screening activities will not be enrolled. Eligibility may be discussed by phone after screening is complete and at the time Visit 3 is scheduled but the final confirmation will occur at Visit 3. If all inclusion criteria and no exclusion criteria are met, eligibility will be confirmed with the subject.

- Complete a final review of inclusion/exclusion criteria.
- Assess general wellbeing.
- Confirm eligibility and willingness to participate in study.
- Enroll subject and issue subject number.
- Ensure medical history and medication history is complete. After enrollment new events will be collected as AEs and new medications, as described in Section 8.5 and Section 9.0.
- Assess status of symptoms at baseline specific to the study population.
- Discuss medication tapering, if applicable. Upon confirmation of eligibility, the PI will consult the prescribing physician to initiate medication tapering for

subjects who must refrain from taking a psychiatric medication for the study. Tapering will follow a time course appropriate for the medication given its half-life, with the first experimental session scheduled to occur after complete washout.

The subjects will undergo three preparatory sessions lasting approximately sixty minutes each with their therapist team, prior to their first experimental session. The first preparatory session will take place at Visit 1 after enrollment confirmation. Baseline measures will be spread out among preparatory sessions in order to reduce participant fatigue from completion of measures.

The therapists will work with the subject to prepare for MDMA-assisted therapy. The therapists and subject will seek to form a strong working relationship with each other as the therapists help the subject prepare for upcoming experimental sessions. Preparatory sessions will promote a safe set and setting for confronting emotions and are intended to develop therapeutic alliance.

During preparatory sessions:

- a. Therapists may record all sessions to audio and video. Subjects may access video recordings from these sessions upon request via a secure and password protected website.
- b. Collect AEs and medications, as described in Section 8.5 and Section 9.0.
- c. Assess status of symptoms at baseline specific to the study population.

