8.6 Baseline Values

Baseline values are from screening/baseline visit for all measures, except C-SSRS. For C-SSRS, baseline (visit 2) scores will be used as a measure of 'lifetime' suicidal ideation and behavior, and preparatory session 3 (visit 5) will be used as 'baseline.'

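### The LSAS effect size is estimated from change scores alone, so in a trial of 8 versus 4 it carries part of any chance baseline imbalance; an ANCOVA on baseline LSAS should be prespecified

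*SAP*

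**What the plan says.** SAP 8.10.1 defines the primary endpoint as LSAS change from baseline to Visit 13, one month after the second experimental session. On the test it says: "The primary efficacy comparison on difference scores will be made with independent sample t-tests at an alpha level of 0.05". SAP 8.0 adds: "All statistical tests will be two-sided". The fallback is a Wilcoxon rank-sum test, and Cohen's d with confidence intervals is taken from the same change scores. None of these has a baseline covariate. SAP 8.10.2 carries the method over to the secondary scales and the biomarkers.

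On allocation, SAP 2.0 says: "eight subjects (66.7%) will be randomized to the MDMA group and four subjects (33.3%) will be randomized to the placebo group". Randomization is 4:2 within each of the two dose groups, and the documents describe no stratification on LSAS.

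Baseline LSAS will exist for every subject. Among the screening steps, Protocol 5.2.1 lists: "A blinded IR will administer the LSAS". Protocol 5.2.2 says: "Subjects who do not complete all screening activities will not be enrolled". SAP 8.6 takes that visit as baseline: "Baseline values are from screening/baseline visit for all measures, except C-SSRS".

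Protocol 12.0 does raise chance differences between arms: "However, owing to small sample size, such variations may arise by chance". The sentence refers to gender, race or ethnicity, duration of diagnosis and psychiatric comorbidity. The stated response is to take a differing demographic variable into account in the safety analyses. Baseline LSAS is not discussed there.

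**The concern.** Subtracting baseline assumes that a subject who starts one point higher would, untreated, also finish one point higher. If the true slope is below 1, high starters tend to fall back towards the mean. The arm with the higher baseline by chance then appears to improve more, whatever the treatment does.

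With only four placebo subjects, a sizeable baseline difference is likely. Protocol 3.1 makes estimation of the LSAS effect size the primary objective, and Protocol 12.0 and SAP 6.0 intend the effect sizes for planning later studies. An estimate moved by baseline imbalance would therefore pass into the next trial's sample size.

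**Working it through.** **Inputs from the documents:** 8 versus 4 subjects (SAP 2.0); one change score per subject, unadjusted, alpha 0.05, two-sided (SAP 8.10.1 and 8.0).

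**Assumptions:** the documents give no LSAS SD and no correlation r between baseline and Visit 13. Results are in baseline-SD units, with normal data, equal SDs at both visits (so the true slope equals r) and r from 0.3 to 0.9. There is no power or sample-size figure in the plan to reproduce.

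**1. Size of the chance imbalance D (MDMA minus placebo).**
- SD of D = √(1/8 + 1/4) = √0.375 = 0.612.
- Mean |D| = 0.612 × √(2/π) = 0.489.
- P(|D| > 0.5) = 0.41, from z = 0.5/0.612 = 0.82.
- P(|D| > 1) = 0.10, from z = 1/0.612 = 1.63.

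**2. Effect on the change-score estimate.** Given D, the estimated difference in change moves by −(1 − r)D. The shift exceeds 0.5 SD when |D| > 0.5/(1 − r).

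| r | Mean absolute shift = (1 − r) × 0.489 | \|D\| needed for a shift above 0.5 SD | Probability |
|---|---|---|---|
| 0.3 | 0.34 | 0.71 | 0.24 |
| 0.5 | 0.24 | 1.00 | 0.10 |
| 0.7 | 0.15 | 1.67 | under 0.01 |

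**3. Error rate.** In simulation (200,000 trials per r), both methods hold type I error at about 0.05 over all randomizations. Among trials with |D| > 1 SD, the change-score t-test rejects a true null in about 0.16, 0.125 and 0.09 of cases at r = 0.3, 0.5 and 0.7. ANCOVA stays at about 0.05.

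**4. Precision.** Expected variance of the estimated difference:
- Change score: 2(1 − r) × 0.375.
- ANCOVA: (1 − r²) × 0.375 × (1 + 1/8). The factor 1/8 is the cost of estimating the slope with 10 within-arm degrees of freedom.
- Ratio, ANCOVA to change score: (1 + r)/2 × 9/8. This equals 0.73 at r = 0.3, 0.84 at 0.5, 0.96 at 0.7, 1.01 at 0.8 and 1.07 at 0.9, and it reaches 1 at r = 0.78.

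The confidence interval also pays for the change from 10 to 9 degrees of freedom. Simulated mean width of the 95% interval, ANCOVA relative to change score:

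| r | 0.3 | 0.5 | 0.7 | 0.75 | 0.8 | 0.9 |
|---|---|---|---|---|---|---|
| Ratio | 0.86 | 0.93 | 0.99 | 1.00 | 1.02 | 1.04 |

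At r = 0.5 the mean half-widths are 1.33 SD (change score) and 1.23 SD (ANCOVA).

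**5. Power.** For a true effect of one baseline SD at r = 0.5, power is 0.32 with the t-test and 0.36 with ANCOVA. The t-test needs an effect of about 1.90 SDs of change for 80% power.

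**The case against.** The strongest reply is that the planned analysis is sound and the gain from changing it is modest. Much of this stands.

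- **Validity.** A reader might infer that baseline LSAS is ignored, or that the t-test is biased or invalid. Neither follows. The difference score uses every subject's baseline, and the test is unbiased and holds its alpha over randomizations. The fault is conditional: it concerns the one imbalance that occurs.
- **Protocol 12.0.** A reader might also infer that the sponsor foresaw LSAS imbalance and confined the remedy to safety. The text does not support this. It concerns demographic and diagnostic characteristics, expects no systematic differences, and says only that chance differences may arise.
- **Size.** The variation from imbalance is already inside the planned confidence interval, which is very wide by either method. A shift above 0.5 SD is uncommon at r = 0.5 and rare at r = 0.7. In a single trial the ANCOVA interval is wider than the change-score interval about 39% of the time at r = 0.5 and 54% at r = 0.7.
- **Robustness.** ANCOVA adds a common linear slope. With 12 subjects the estimated slope has an SD of about 0.31 at r = 0.5.
- **Status.** The SAP calls the study exploratory, makes no power claim and permits labelled post-hoc analyses.

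What does not stand is the inference that nothing need change. Exploratory status explains low power and the absence of multiplicity control. It is no reason to prefer an estimate that moves with baseline imbalance when estimation is the purpose. A post-hoc adjustment, chosen after the imbalance is seen, would also be less credible than a prespecified one.

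**Conclusion.** The concern holds as a conditional-bias point about the planning effect size, not as a claim that the primary test is wrong. For r between 0.3 and 0.7, chance imbalance moves the estimate by 0.34 to 0.15 baseline SD on average, towards the arm that starts higher. ANCOVA removes this shift at every r below 1 under a linear, common-slope model. Its effect on precision depends on r, from a 14% narrower mean interval at r = 0.3 to a 4% wider one at r = 0.9, with break-even near 0.75. These figures rest on normal data, equal SDs at the two visits and an r that the documents do not supply. The change is worth making because the covariate is already collected, but it will not make a 12-subject estimate precise.

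**What to change.** In SAP 8.10.1:

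1. Make the primary estimate an ANCOVA of Visit 13 LSAS on arm and baseline LSAS, reported as the adjusted mean difference with a 95% confidence interval.
2. State the SD used to standardize that difference, for example the pooled baseline SD, and also report the planned Cohen's d on change scores.
3. Keep the change-score t-test as a sensitivity analysis, and the Wilcoxon test as the fallback if the parametric assumptions fail.
4. In SAP 8.10.2, use the same model for secondary scales that have both a baseline and a Visit 13 value.

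The cost is SAP wording only; no new data are needed. The statistical price is one degree of freedom, an imprecisely estimated slope, a linearity assumption that 12 subjects can barely check, and a slightly wider interval on average if r exceeds about 0.75. Reporting both analyses covers that case.
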